12.2.12.5. Health State Utility

The EQ-5D 5L data will be scored as described in an article that is under review for publication (van Hout et al. 2012). The index score is calculated from a set of item weights to derive a score of 0 to 1, with 1 representing the best health status. Geographic-specific weights will be used as appropriate and when available. The VAS is scored from 0 (*worst imaginable health state*) through 100 (*best imaginable health state*) to represent the patient's self-report for each day. EQ-5D 5L responses for each item will be summarized by frequency and corresponding percentages. Descriptive statistics for the index and VAS will be calculated. Psychometric analyses, including calculation of reliability coefficients (Cronbach's alpha), will also be performed. The index scores and VAS may be analyzed using a mixed effects analysis of variance model. Of interest is a significant time-by-group interaction for each of the items, addressing whether treatment group profiles are different over time (from randomization through the last assessment following discontinuation).

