Reference Therapy, Dose, and Mode of Administration: Placebo will be supplied by the sponsor to be administered orally Q12H on Days 1 to 28 of a 28-day cycle plus fulvestrant will be administered 500 mg intramuscularly into the buttocks slowly (1 to 2 minutes per injection) as two 250-mg injections, one in each buttock, on Days 1 and 15 of Cycle 1, then on Day 1 of Cycle 2 and beyond.

Criteria for Evaluation:Efficacy:

- PFS
- OS
- OS at 1, 2, and 3 years
- Objective Response Rate
- DoR
- DCR

Safety:

- Adverse events

Health Outcomes:

- BPI: proportion of patients with “worst pain” increase of 2 points or more at any time on-therapy, compared to baseline
- EORTC QLQ-C30 and EORTC QLQ-BR23: Describe target tumor symptom changes
- EQ-5D 5L: Describe health status changes

Pharmacokinetics:

- Population PK parameters for abemaciclib and fulvestrant
- Plasma concentration levels of fulvestrant during Cycle 1/Cycle 2

Exploratory

- Potential biomarkers related to the Rb pathway and/or the pathogenesis of breast cancer.
- Time course of change in tumor size
- Time from randomization to documentation of the first occurrence of any SRE
- Time from randomization to documentation of the first occurrence of any PS of ≥ 2

Statistical Methods:

Statistical: The primary objective of this study is to compare abemaciclib plus fulvestrant versus placebo plus fulvestrant in terms of PFS for women with HR+, HER2- locally advanced or metastatic breast cancer. An important secondary objective of this study is to compare the 2 arms with respect to OS.

A 2-look group sequential design on the primary endpoint of PFS will be utilized, with 1 interim analysis and 1 final PFS analyses occurring at approximately 265 and 378 investigator-assessed PFS events in the EP stratum.

A fixed alpha-spending method will be used to maintain the cumulative 1-sided Type I error rate of .025.

Assuming a hazard ratio (HR) of 0.703, this design yields approximately 90% statistical power to detect superiority of the abemaciclib plus fulvestrant arm over placebo plus fulvestrant arm with the use of a 1-sided log-rank test and a cumulative type I error rate of 0.025.

OS is an important secondary endpoint for this study. OS will be tested only if the test of PFS is significant. The final OS analysis will be performed when approximately 441 OS events have been observed in the EP stratum.

Efficacy:

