6.2. Secondary Objectives

The secondary objectives of the study are to compare abemaciclib plus fulvestrant versus placebo plus fulvestrant with respect to each of the following:

- overall survival (OS)
- OS rate at 1, 2, and 3 years
- objective response rate [complete response (CR) + partial response (PR)]
- duration of response (DoR) [CR + PR]
- disease control rate (DCR) [CR + PR + stable disease (SD)]
- clinical benefit rate (CBR) [CR + PR + SD \geq 6 months]
- safety and tolerability
- pain and symptom burden using the Brief Pain Inventory (BPI), the European Organization for Research and Treatment of Cancer Quality of Life Questionnaire-Core 30 (EORTC QLQ-C30) and the EORTC QLQ-BR23 (breast) questionnaires, and health status scores from the EuroQol 5-Dimension 5 Level (EQ-5D 5L)
- pharmacokinetics (PK) of abemaciclib, its metabolites, and fulvestrant

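### The only inferential EQ-5D result named is a time-by-group interaction, which tests for parallel profiles and does not estimate the between-arm difference in health status

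*Protocol*

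**What the plan says.** Protocol Section 6.2 lists, among the outcomes on which the arms are to be compared, "health status scores from the EuroQol 5-Dimension 5 Level (EQ-5D 5L". The synopsis criterion is weaker: "EQ-5D 5L: Describe health status changes".

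Section 12.2.12.5 gives the analysis. For the items: "EQ-5D 5L responses for each item will be summarized by frequency and corresponding percentages". For the two scores: "Descriptive statistics for the index and VAS will be calculated". Then comes an optional model: "The index scores and VAS may be analyzed using a mixed effects analysis of variance model". The result sought from it is stated next: "Of interest is a significant time-by-group interaction for each of the items, addressing whether treatment group profiles are different over time", over a period running "from randomization through the last assessment following discontinuation".

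No group effect, average difference, visit-specific difference or change from baseline between arms is named for EQ-5D. The maximum-change summary in Section 12.2.12 covers BPI worst pain and the EORTC composite scores only. Section 12.2.2 sets tests of interactions at a two-sided 0.10 and tests of treatment effects at 0.05, unless otherwise stated. Section 12.2.12 defers further detail to the SAP. The only SAP document supplied is the overall survival addendum, which does not mention EQ-5D.

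**The concern.** The null hypothesis of a time-by-group interaction is that the two mean profiles are parallel. The comparison listed in Section 6.2 is about the level of health status. The two differ in three ways.

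- A steady benefit or harm is not what the interaction is built to find. At best, its signal is spread over one degree of freedom per post-baseline visit.
- Profiles that cross, with no difference on average, give a significant interaction.
- A multi-degree-of-freedom interaction has no sign and no single effect estimate. Section 10.2.1.3 wants the utilities as input to economic evaluations, which need both.

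The neighbouring sections do name direct comparisons: a repeated-measures comparison of pain scores between arms (12.2.12.1), a log-rank test of time to worsening in pain (12.2.12.2), and between-arm comparison of QLQ-C30 scales (12.2.12.3). EQ-5D is the exception.

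The sentence also does not match its own model. The model is for the index and VAS, while the interaction is sought for the items, which are otherwise only tabulated.

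**Working it through.** **The plan's own power figure.** The documents state power only for PFS (Protocol Section 12.1: 378 events, hazard ratio 0.703, 2:1 allocation, one-sided 0.025, about 90%). Check: √(378 × 2/9) × |ln 0.703| − 1.96 = 9.165 × 0.3524 − 1.96 = 1.27, and Φ(1.27) = 0.898. It reproduces. No power is stated for EQ-5D.

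**Inputs from the protocol.**
- 630 patients at 2:1, so 420 and 210 (Section 8.1).
- EQ-5D at baseline and Cycles 2, 3, 5, 7, 9, 11 and 13 (Attachment 1, footnote k). Later visits and short-term follow-up are left out of the calculation.
- Median PFS 6.5 months on control (Section 12.1), and 6.5/0.703 = 9.25 months on abemaciclib. These are used only to model loss of questionnaires. At Cycle 13, 12 × 28 days = 11.04 months, so the fractions remaining are exp(−ln 2 × 11.04/9.25) = 0.44 and exp(−ln 2 × 11.04/6.5) = 0.31.

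**Assumptions not in the documents.** A steady post-baseline difference of 0.15 to 0.3 SD; within-patient correlation either compound symmetry (CS) 0.5 to 0.7, or AR(1) 0.8 between successive visits; monotone exponential loss.

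**Method.** Let δ be the vector of between-arm differences by visit and C its covariance, the sum of the inverses of the two arms' expected information matrices. For contrasts L, the noncentrality is λ = (Lδ)′(LCL′)⁻¹(Lδ), and power comes from the noncentral chi-square distribution. The interaction with baseline as a level of time has 7 df. The average post-baseline difference, given baseline, has 1 df.

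**Hand check with no loss, CS 0.5, 0.2 SD, alpha 0.05.** The effective size is 1/(1/420 + 1/210) = 140.
- Interaction: δ = (0, 0.2 × 7), mean 0.175, sum of squares 0.175² + 7 × 0.025² = 0.035. λ = 140 × 0.035/(1 − 0.5) = 9.8 on 7 df, power 60%.
- Average: variance (1 + 6 × 0.5)/7 − 0.5² = 0.321. λ = 140 × 0.04/0.321 = 17.4 on 1 df, power 99%.

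**Results with loss, 0.2 SD.**

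| Correlation | Interaction, 0.05 | Interaction, 0.10 | Average difference, 0.05 |
|---|---|---|---|
| CS 0.5 | 53% | 65% | 94% |
| CS 0.6 | 64% | 75% | 96% |
| CS 0.7 | 78% | 86% | 98% |
| AR(1) 0.8 | 77% | 85% | 84% |

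**Other effect sizes.** At 0.15 SD, the interaction has 30-49% at alpha 0.05 and the average difference 60-86%. At 0.3 SD, the interaction has 91-99% at 0.05 and at least 95% at 0.10, and the average difference over 99%.

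**Other codings.** With linear time including baseline, the interaction has 27-42% power at 0.2 SD and alpha 0.05. With post-baseline visits alone and baseline as a covariate, a constant difference gives parallel profiles, λ = 0, and power equals alpha at every effect size.

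**Reverse case.** An effect running from −0.3 to +0.3 SD with zero average (CS 0.6) gives about 100% power for the interaction and 5% for the average difference. A significant interaction therefore does not show which arm fares better.

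**The case against.** The strongest reply is that the profile is said to start at randomization, and the questionnaire is given at baseline. Baseline is then most naturally a level of time. Randomized arms start equal in expectation, so a steady post-baseline shift is itself non-parallel and the interaction can detect it. This stands. A reader might infer that the test has no power against a steady difference. That needs a model with post-baseline visits alone and baseline as a covariate, and Section 12.2.12.5 mentions no covariate. It does not fix the coding of baseline and time either.

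The relevant alpha may also be 0.10 rather than 0.05, since Section 12.2.2 covers all interactions unless otherwise stated. This stands too, and it narrows the gap.

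The steady effect is an assumption. Section 5.1.1 reports dose alterations caused mainly by diarrhea in the first treatment cycle, so an effect that changes over time is plausible. For such a pattern the interaction is useful and an average alone can fail. That argues for reporting both. It does not make the interaction the between-arm comparison.

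A mixed ANOVA would ordinarily also print a group effect and visit means. The plan does not name them as the comparison. If baseline is a time level, the usual group main effect averages in a visit at which no treatment difference is expected.

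Finally, the model is optional, the synopsis asks only for description, and the full SAP (version 4, cited in the addendum) was not supplied and may name another contrast. These points limit the consequence.

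**Conclusion.** The point holds for the supplied documents: the one inferential EQ-5D result named does not estimate the between-arm difference listed in Section 6.2, and it is attached to the items although the model is for the index and VAS.

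Under the assumptions above, with baseline as a level of categorical time, the cost for a steady 0.2 SD difference is power of 53-78% at alpha 0.05, or 65-86% at 0.10, against 84-98% for the adjusted average difference at 0.05. Under AR(1) 0.8 the gap is 77% against 84% with both tests at 0.05, and disappears with the interaction at 0.10 (85% against 84%). At 0.3 SD with alpha 0.10 little is lost. The absence of direction and size does not depend on these assumptions.

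A reader might also infer that the secondary objective goes unanswered. The documents do not support that. The planned descriptive statistics for index and VAS can show direction and approximate size, and the unseen SAP may add a contrast. What is affected is an optional secondary patient-reported analysis. No power statement or primary conclusion depends on it.

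**What to change.** Check first whether SAP version 4 already names a between-arm contrast for EQ-5D. If it does not, amend Section 12.2.12.5, or state the change in the SAP, as follows.

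- Make the between-arm EQ-5D result the baseline-adjusted average post-baseline difference in index and in VAS from the planned mixed model, over a fixed visit window (for example Cycle 2 through Cycle 13), with a two-sided 95% CI.
- State that baseline is handled by adjustment and not as a level of time.
- Keep the time-by-group interaction and visit-wise means as secondary description, and state the alpha for the interaction.
- Replace the reference to the items with the index and VAS. The items remain summarized by frequency.

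The cost is a few lines of text and one contrast from a model already planned, with no new data, visits or patients. The downside is that an average can hide an early-late reversal, which the retained interaction and visit means would show.

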12.2.12.6. Exploratory Analyses

Joint modeling may be explored to characterize the relationship between features of the longitudinal PRO trajectories (individual items or composite scores) and the event times.

Time from randomization to earliest development of new bone metastases may be analyzed and compared between arms.

Proportion of patients who experience a "worst pain" increase of ≥ 2 points at any post-baseline visit (on or after Day 1 Cycle 2) will be compared between treatment arms. Changes in analgesic and bone agent use will be collected and summarized by arms.

Time from randomization to documentation of the first occurrence of any SRE will be evaluated. Patients not known to have had an SRE at the time of the analysis will be censored at the date of their last complete documented assessment for SRE. A log-rank test will be used to evaluate the difference of time to first SRE between treatments. Impact of other factors, including whether a

patient had at least 1 SRE prior to randomization as well as those factors used to stratify treatment randomization, will be explored.

Time from randomization to documentation of the first occurrence of any PS of ≥ 2 will be evaluated. Log-rank test will be used to evaluate the difference of time to worsening in ECOG PS between treatments.

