The PFS and OS analyses to test the superiority of abemaciclib to placebo in improving PFS and OS time will use the log-rank test stratified by stratification variables. Additional analyses will be performed using the Kaplan-Meier method to estimate the PFS and OS curves and rates, and the Cox proportional hazard model will be used to estimate the PFS and OS HRs and corresponding 95% confidence interval.

Safety:

All safety summaries and analyses will be based on the Safety Population. Patients will be grouped according to treatment received in Cycle 1.

Health Outcomes:

The maximum change from baseline score will be calculated and summarized for BPI “worst pain” and EORTC composite scores. The number and reason for missing and incomplete questionnaires/assessments will be summarized for each instrument and study arm.

Pharmacokinetics:

PK parameters for abemaciclib in plasma (clearance, exposure, volume of distribution, and half-lives) and inter-individual PK variability will be computed using nonlinear mixed effect modeling implemented in NONMEM. If warranted by the data, PK parameters for fulvestrant in plasma and inter-individual variability estimates will also be computed using nonlinear mixed effect modeling implemented in NONMEM.

Pharmacodynamics:

Pharmacodynamic data (such as neutrophil, lymphocytes, or platelets counts in blood) may be analyzed by means of NONMEM and connected to the population PK model for abemaciclib and/or fulvestrant in a PK/pharmacodynamic model.

Tailoring biomarkers:

Summary statistics will include means, medians, corresponding standard errors, quartiles, and ranges. Biomarkers with discrete measures, such as genotype locus, will be summarized in frequency tables. Correlative analyses may be performed to investigate associations between biomarkers and clinical endpoints.

3. Table of Contents

MONARCH 2: A Randomized, Double-Blind, Placebo-Controlled, Phase 3 Study of Fulvestrant with or without Abemaciclib, a CDK4/6 Inhibitor, for Women with Hormone Receptor-Positive, HER2-Negative Locally Advanced or Metastatic Breast Cancer

Section	Page
1. Protocol I3Y-MC-JPBL(g) MONARCH 2: A Randomized, Double-Blind, Placebo-Controlled, Phase 3 Study of Fulvestrant with or without Abemaciclib, a CDK4/6 Inhibitor, for Women with Hormone Receptor-Positive, HER2-Negative Locally Advanced or Metastatic Breast Cancer.....	1
2. Synopsis	2
3. Table of Contents.....	7
4. Abbreviations and Definitions.....	14
5. Introduction	19

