12.1. Determination of Sample Size

The primary objective of this study is to compare abemaciclib plus fulvestrant versus placebo plus fulvestrant in terms of PFS for women with HR+, HER2- locally advanced or metastatic breast cancer.

This study will enroll 2 strata of patients according to prior endocrine therapy: endocrine therapy pretreated (EP) patients and endocrine therapy naïve (EN) patients.

The primary statistical analyses will be performed on patients in the EP stratum.

The initial study protocol specified an enrollment of 450 EP patients. Amendment (a) changed the starting dose of blinded study drug from 200 mg Q12H to 150 mg Q12H. In addition to describing the safety profile in the full EP safety population, safety analyses will be conducted in the subgroup of patients enrolled under Amendment (a) with a starting dose of 150 mg Q12H. In order to do this robustly, enrollment to the study will continue until 450 EP patients are enrolled at a starting dose of 150 mg Q12H. As of the implementation of Amendment (a), approximately 180 EP patients had been enrolled at a starting dose of 200 mg Q12H. Including these 180 patients, the final size of the EP stratum will be approximately $450 + 180 = 630$ patients.

Patients will be randomized in a 2:1 ratio using the following stratification factors: nature of disease (visceral metastases versus bone only metastases versus other) and sensitivity to endocrine therapy (primary resistance versus secondary resistance).

A 2-look group-sequential design of the primary endpoint will be used to accommodate an event-driven plan for the interim and final PFS analyses (see Section 12.2.7 for details). The final PFS analysis will be performed after 378 PFS events have occurred in the EP stratum (that is, a 40% censoring rate). Assuming a hazard ratio (HR) of 0.703, this sample size yields approximately 90% statistical power to detect superiority of the abemaciclib plus fulvestrant arm over the placebo plus fulvestrant arm with the use of a 1-sided log-rank test and a type I error of 0.025. If the true median PFS for the placebo plus fulvestrant arm is 6.5 months, then the HR of 0.703 amounts to an approximately 2.75-month (42%) improvement in median PFS for the abemaciclib plus fulvestrant arm under an additional assumption of exponential survival distribution.

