12.2.12.2. Pain Assessment

Pain analysis will be based on all randomized patients with at least 1 baseline BPI “worst pain” and one BPI “worst pain” score on Cycle 2 Day 1 or later.

The mBPI-sf will be administered at baseline prior to study drug dosing and the Cycle 1, Day 1 score will be treated as a baseline observation and the Day 1 score of each subsequent cycle will be attributed to the previous cycle. The mBPI-sf will be administered at treatment discontinuation and grouped with observations from the previous cycle.

Time to worsening in pain will be described using the method of Kaplan and Meier and will be made between 2 arms by a log-rank test. “Worsening” will be defined as either a “worst pain” increase of ≥ 2 points postbaseline or an analgesic drug class increase of ≥ 1 level. Worsening rate at Years 1, 2, and 3 will be estimated and compared between the 2 arms. Number of events due to each criterion will be described.

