- j One or more of these studies [X-ray, CT scan with bone windows, or MRI] is performed locally at baseline (Day -28 to Day -1), between Day 1 and Day 7 of every second cycle beginning with Cycle 3 and continuing through Cycle 13, between Day 1 and Day 7 of every third cycle after Cycle 13, and within 14 days of clinical progression only for patients with bone lesions identified by bone scintigraphy at baseline. To allow flexibility in tumor assessments, imaging conducted up to 3 days prior to Day 1 of the predefined cycles (as early as Day 26 of the prior cycle) will not be considered a protocol deviation. For patients with new lesions identified by post-baseline bone scintigraphy, targeted assessment by X-ray, CT scan with bone windows, or MRI will be performed to confirm findings. For patients who discontinue study treatment without objectively measured progressive disease (PD), continue to evaluate tumor response approximately every 8 weeks for the first 12 months following randomization and thereafter approximately every 12 weeks by the same method used at baseline and throughout the study until the patient has objective disease progression or until study completion. After the patient has objective disease progression, radiologic tests are no longer required and the patient will continue with post-discontinuation follow-up until the patient's death or overall study completion.
- k mBPI-sf, EORTC QLQ-C30, EORTC QLQ-BR23 and EQ-5D 5L should be administered at baseline (Day -14 to Day -1), Cycle 2 Day 1, and then on Day 1 of every second cycle beginning with Cycle 3 and continuing through Cycle 13, on Day 1 of every third cycle after Cycle 13, and at Short-Term Follow-Up. Patients should complete these assessments before extensive interaction with site staff.
- l Skeletal-Related Events include pathological fracture, spinal cord compression, radiation to bone, and surgery to bone.
- m See Pharmacokinetic Sampling Schedule ([Attachment 7](#)).
- n FSH and estradiol levels are required only for women age <60 years and amenorrheic for at least 12 months.
- o A serum pregnancy test is required only for patients receiving ovarian suppression with a GnRH agonist.
- p For Cycle 2 and beyond, the start of a cycle may be delayed up to 7 days for logistical reasons and up to 14 days to allow sufficient time for recovery from toxicity possibly related to a study drug. Refer to Section [9.4.1.1.2](#).

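### If abemaciclib patients stay on treatment longer, an excess on abemaciclib in Section 12.2.12.6's any-visit pain proportion cannot be read as a pain effect

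*Protocol*

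**What the plan says.** - **The comparison.** Protocol Section 12.2.12.6 says the proportion with a worst-pain rise of 2 or more "points at any post-baseline visit (on or after Day 1 Cycle 2) will be compared between treatment arms". This is a commitment, whereas joint modeling in the same section is optional. No end of window, exposure adjustment or test is named. The general default in Section 12.2.2 is a 2-sided 0.05 level.
- **When pain is measured.** Attachment 1, footnote k, schedules the questionnaires at baseline, Cycle 2 Day 1, every second cycle from Cycle 3 through Cycle 13, then "on Day 1 of every third cycle after Cycle 13, and at Short-Term Follow-Up". Section 12.2.12.2 describes the closing assessment differently: "The mBPI-sf will be administered at treatment discontinuation".
- **How long treatment lasts.** The Synopsis and Section 7.3.1 end treatment at progression or for another discontinuation reason. Section 12.1 assumes a placebo median PFS of 6.5 months and a hazard ratio of 0.703, an "approximately 2.75-month (42%) improvement in median PFS for the abemaciclib plus fulvestrant arm".
- **The Synopsis.** Its BPI criterion is the proportion with a worst-pain "increase of 2 points or more at any time on-therapy, compared to baseline". Its methods text plans no test of that proportion: "The maximum change from baseline score will be calculated and summarized for BPI" worst pain and the EORTC composites.
- **What else is planned.** Section 12.2.12.2 defines worsening as a 2-point rise or a step up in analgesic class, uses Kaplan-Meier, and says the comparison "will be made between 2 arms by a log-rank test". It adds: "Number of events due to each criterion will be described".
- **What is deferred.** Section 12.2.12 leaves further detail to the main SAP, which is not among the documents. The supplied SAP addendum covers overall survival only.

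**The concern.** The probability of ever observing a 2-point rise grows with the number of times pain is measured. Here that number depends on time on treatment, which the trial is designed to lengthen in one arm. Two arms with identical pain could therefore differ on this measure.

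Section 10.2.1 makes palliation of pain the main health-outcomes goal. A spurious excess of worsening on abemaciclib would bear directly on that goal and could be reported as harm. If pain instead rises mainly when treatment ends, the any-visit proportion can miss a real delay, because it ignores when the rise occurred.

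**Working it through.** **1. The plan's own figures (Section 12.1).** Power = Φ(√(378 × 1/3 × 2/3) × |ln 0.703| − 1.96) = Φ(9.165 × 0.3524 − 1.96) = Φ(1.27) = 0.898, which matches the stated 90%. The abemaciclib median is 6.5/0.703 = 9.25 months, a gain of 2.75 months (42%).

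**2. Assessments per patient.** Assumptions: time on treatment equals PFS and is exponential, S(t) = 0.5^(t/median), with 24 months of follow-up. Scheduled days are 28, 56, 112, 168, 224, 280, 336, 420, 504, 588 and 672.
- The sum of S(t) over these days is 4.72 on placebo and 5.81 on abemaciclib.
- Among patients with at least one on-treatment score: 4.72/0.907 = 5.2 against 5.81/0.933 = 6.2.
- With a closing assessment for patients whose treatment ends within 24 months (92.3% and 83.5%): 4.72 + 0.92 = 5.6 against 5.81 + 0.83 = 6.6.
- With follow-up uniform over 6 to 22 months, the counts are 4.5 against 5.1, or 4.8 against 5.4 with the closing assessment.

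**3. A check by hand.** Suppose each assessment carries the same chance q of a first rise in both arms, and every patient has the closing assessment. Then P(any rise) = 1 − (1 − q)[1 − Σ q(1 − q)^(k−1) S(t_k)].
- For q = 10% the sums are 0.355 and 0.417, giving 41.9% on placebo and 47.6% on abemaciclib, an excess of 5.6 points before rounding.
- With 210 and 420 patients the standard error is √(0.457 × 0.543 × (1/420 + 1/210)) = 0.042, so z is centered near 1.33. A falsely adverse result has probability 1 − Φ(1.96 − 1.33) = 0.26.
- For q from 3% to 15%, follow-up of 12 to 36 months and other discontinuation of 0 or 2% per month, the excess is 1.3 to 6.9 points. A nominal 5% two-sided test rejects in 6% to 37% of trials.
- In simulation (24 months, q from 5% to 15%, on-treatment visits), a log-rank test of time to first rise rejects in 4.6% to 4.9%.

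**4. A more realistic score model.** Constant risk probably overstates the effect. With stable pain, patients whose baseline score happened to be low tend to show a rise early, so later visits add less. Simulated scores were mean + patient effect + autocorrelated error, rounded and limited to 0–10. The main grid used mean 3, between-patient SD 2.4, within-patient SD 1 or 2, and autocorrelation 0.3 or 0.6. These values are assumptions; the documents give none. The comparison is a pooled two-proportion z-test with 420 against 210 patients. Nominal is 2.5% per direction.
- Stable pain, time-on-treatment hazard ratio 0.703: repeated runs give an excess of about 1.2 to 4.2 points and a falsely adverse result in about 5% to 16% of trials. The larger values come with 24 months of follow-up.
- Stable pain, other hazard ratios: falsely adverse in 5.4–9.0% at 0.8, 3.1–6.0% at 0.9 and 1.8–2.9% at 1.0. At 1.1 the bias reverses, with falsely favorable results in 3.6–5.1%.
- Hazard ratio 0.703, worst pain 1 point higher at the visit after treatment ends: excess −0.3 to +3.0 points, adverse in 2.6–10.2%. With 2 points: −3.7 to +1.8 points, adverse in 0.2–5.5%.
- Hazard ratio 0.8 with either rise: excess −2.5 to +1.9 points, adverse in 0.7–7.2%.

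**5. The log-rank alternative** (first 2-point rise, censored at the last assessment). With stable pain and hazard ratio 0.703 it is adverse in 1.1–2.6% and favorable in 2.4–4.1% of trials. Where pain rises at treatment end, worsening really is later on abemaciclib. The log-rank test then favors abemaciclib in 5.5–14.0% (1 point) and 9.0–46.4% (2 points) of trials; the any-visit test does so in 0.5–2.7% and 0.8–14.2%.

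**The case against.** The comparison is exploratory, no alpha is allocated to pain in these documents, and no test is named for it. The two-proportion test above is a reasonable reading of the Section 12.2.2 default, not a stated method. Section 12.2.12.2 already plans a log-rank analysis of worsening with rates at Years 1, 2 and 3. Section 12.2.12.5's neighbor, 12.2.12.6, also allows joint modeling, and Section 12.2.12.1 allows a repeated-measures model. The main SAP may set a window. Stable pain is the setting that shows the bias most clearly. The log-rank contrast in step 5 is partly built in, because the rise was placed at treatment end. Whether pain ever worsened and when it worsened are also different questions.

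All of this limits the reach of the point. It does not supply a common window. The Section 12.2.12.2 endpoint is a composite with analgesic steps, so the worst-pain-only comparison has no time-to-event counterpart, although Section 12.2.12.6 itself uses log-rank tests for skeletal events and performance status.

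A reader might infer that the sign of the comparison says nothing about pain in either direction. The documents do not support that. If longer exposure on abemaciclib is the only bias, it works against abemaciclib, so a lower proportion there would arise despite it and stays informative. In the constant-risk model at 24 months, the expected sign favors abemaciclib once the true per-assessment risk ratio falls below about 0.83. Nor is the direction of bias certain: Section 7.3.1 lets treatment end by investigator or patient decision, so time on treatment need not follow PFS.

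A reader might also infer that the Synopsis makes this proportion a formally tested pain endpoint. It plans no test of it, and which BPI measure it lists is a matter of presentation.

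**Conclusion.** The point holds conditionally. As written, the any-visit comparison favors whichever arm is assessed less often. If treatment lasts longer on abemaciclib, an excess there cannot be taken as worse pain. The size, roughly 1 to 4 points and 5% to 16% falsely adverse against 2.5%, rests on assumed stable pain, assumed score variability and follow-up, and time on treatment equal to PFS at a hazard ratio of 0.703. The constant-risk model gives a wider range. The bias moves toward zero or reverses if pain rises at treatment end or if treatment is not longer on abemaciclib. The consequence is confined to one exploratory comparison; PFS and OS inference is unaffected. This is a change to consider, and the absence of a window is established only for the documents supplied.

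**What to change.** 1. In Section 12.2.12.6, make the between-arm comparison time to first worst-pain rise of 2 or more points, by Kaplan-Meier and log-rank test, censored at the last pain assessment. Report it beside the composite of Section 12.2.12.2.
2. Keep the any-visit proportion as description only, shown with the number of assessments per arm.
3. Reconcile the Synopsis criterion, which is restricted to the on-therapy period, with Section 12.2.12.6, whose wording would also take in the short-term follow-up assessment.

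If the main SAP already does this, only the protocol wording needs to match. The cost is a few lines of text. No new data are needed, because Section 12.2.12.2 already uses the method and counts events by criterion. The drawback is that the log-rank analysis treats the end of pain assessment as uninformative censoring. That is open to doubt when assessment stops around progression, but Section 12.2.12.2 already makes the same assumption.
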